Subjects who learn of the study through their physician or through advertisement and are interested will be asked to initiate contact with the study staff. Patients who respond to website advertising may elect to fill out a survey regarding eligibility that will ask them to provide contact information if they are willing to be contacted. Alternatively, if a patient's physician obtains the patient's permission for study staff contact, we may contact potential participants who have been identified as suitable by local providers. For patients seen clinically by the PI or other physician investigators involved in the study, the following procedures will be followed to ensure that subjects do not feel obligated to participate because of the involvement of their regular physician: The provider may mention the study to the patient and provide a flyer or consent form for the subject to take home. If this occurs, the provider will not talk further about the study unless the patient initiates the conversation by expressing interest. Alternatively, the patient's provider may mention the study and either ask the patient's permission for a different study provider to contact him/her, or provide contact information of a different study provider whom the patient can contact if interested.

Preliminary eligibility will be determined based on study staff interviews of interested subjects over the phone. Eligible subjects will then be scheduled for a screening visit.

Informed Consent

Written informed consent will be obtained by a licensed physician investigator prior to screening evaluation and testing. Subjects will be informed that they may withdraw from participation in the study at any point.

V. Study Procedures

The study will be conducted over 2 years, with subject recruitment complete after 18 months. Each eligible subject will participate in the study for 24 weeks. Following the screening visit, eligible subjects will return to the Massachusetts General Hospital Clinical Research Center (CRC) for as shown in the schema. Subjects in the Norditropin group will have 7 additional visits, and subjects in the No Treatment group will have 3 additional visits. Subjects who discontinue treatment for any reason will be asked to continue to return for study visits per their original randomization assignment.

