For all female subjects, urine pregnancy tests will be performed at all visits, and a positive pregnancy test will result in immediate discontinuation. At baseline, 12 weeks, and 24 weeks, subjects will be counseled regarding lifestyle modification (see Methods). Subjects will continue to receive care from their regular medical providers, including hepatologists, throughout the study. Any subject not under the care of a hepatologist who is found at screen to have $\geq 5\%$ liver fat and significantly elevated AST or ALT will be offered referral to the hepatology clinic.

Screen: (1) Informed consent; (2) Detailed H&P, including medications and alcohol habits; (3) blood sampling for IGF-1, CBC, HbA1c, fasting glucose, AST, ALT, total bilirubin, Hepatitis B sAg, Hepatitis C antibody; (4) ^1H -MRS/MRI of abdomen in fasting state for quantification of liver fat. (This scan will also be used to assess VAT and SAT for those eligible subjects participating in the baseline visit.)

Randomization and Study Drug: After the screening visit, eligible patients who wish to participate will be randomized in a 1:1 ratio to Norditropin vs. no treatment. The study will not be blinded and placebo will not be used to avoid daily injections without benefit for subjects randomized to no treatment. Randomization will be stratified by gender and Vitamin E use. The starting dose of Norditropin will be 0.5 mg daily, which is a recommended dose for restarting growth hormone in young adults with GHD during the transition from adolescence to adulthood (70). IGF-1 will be checked at 2, 4, 6, 12, and 18 weeks, and will be reviewed by the PI. Active dose adjustments will be performed per algorithm as follows. A 20% dose increase will be performed for any Norditropin subject with IGF-1 SDS ≤ 0 . Conversely, a 20% decrease in dose will be performed for any Norditropin subject with IGF-1 SDS > 2 .

| Norditropin Dosing Algorithm (starting dose 0.5 mg) | | |
|--|-------------------------------|---------------------|
| IGF-1 SDS ≤ 0 | $0 < \text{IGF-1 SDS} \leq 2$ | IGF-1 SDS > 2 |
| 20% dose increase | maintain dose | 20% dose reduction* |
| *Subjects with persistent IGF-1 SDS > 2 after 2 dose reductions will be discontinued from the study. | | |

Baseline Visit:

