Study Drug: For those randomized to treatment, Norditropin (rhGH) will be started at a dose of 0.5mg daily. The GH dosing strategy (see above) is designed to achieve IGF-1 levels between 0-2 SDS. This strategy represents a modification of the dosing strategy in a previous pilot study, which began with 0.4mg daily at baseline, increased to 0.6mg at week 1 and 0.8mg GH daily by week 2, and then included subsequent dose adjustments at 1 and 3 months using the same algorithm proposed above. This strategy resulted in a mean IGF-1 SDS of 0 in the treatment group, and thus proved somewhat too conservative. The recommended dose for restarting GH during the transition period in young adults with GH deficiency is 0.2-0.5mg/day (70). Based on this recommendation and the experience from our previous study, we will start with a baseline dose of 0.5mg and include the opportunity for further adjustments at 2, 4, 6, 12, and 18 weeks. At the Principal Investigator's discretion, subjects receiving Norditropin whose IGF-1 z-score is rising near 2 may be asked to come for an additional blood draw for IGF-1 between 12-24 weeks, to ensure that levels remain below a z-score of 2. Subjects will be instructed to administer Norditropin at night before bedtime. GH was safe and well-tolerated in the previous pilot study. Safety will be closely monitored. Although no dosing reductions were required in the pilot study and we do not anticipate this circumstance, subjects with IGF-1 SDS >2 will undergo a 20% dose reduction. If a subject undergoes 2 dose reductions and continues to have IGF-1 SDS >2, s/he will be discontinued from the study. Subjects with fasting glucose ≥126mg/dL will have the value confirmed on a repeat draw and, if hyperglycemia is confirmed, will be discontinued from the study. Subjects reporting significant adverse effects including significant arthralgia, myalgia, or edema will also be discontinued. These did not occur in the pilot study and are not anticipated to occur with the physiologic dosing strategy that we will utilize.

Compliance will be assessed using a daily study drug diary as well as vial count of returned used and unused study drug.

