Possible side effects of rhGH include headache, edema, myalgia, arthralgia, and hyperglycemia. Subjects will be asked to contact study physicians right away with any potential side effects, and subjects who experience concerning side effects will be advised to discontinue the medication. A physician will be available on-call 24 hours/day, 7 days/week, to all study participants for any questions or concerns. Fasting blood sugar will be checked at 2, 4, 6, and 12 weeks, and any subject with a fasting blood sugar ≥ 126 mg/dL that is confirmed on recheck will be discontinued from the study, with appropriate follow-up to ensure return to euglycemia. RhGH, particularly at physiologic dosing, is incredibly well-tolerated in the pediatric population, and there were no significant GH-related side effects in our pilot study of obese adolescents. When side effects, including hyperglycemia, do occur with rhGH, these resolve with discontinuation of treatment unless there is an underlying, non-GH-related, etiology.

As stated elsewhere, a pregnancy test will be performed at each visit for females able to become pregnant, and subjects will be informed of the study-related risks of pregnancy and the need not to become pregnant during the study. If a subject is found to be pregnant, she will be asked to discontinue the study drug immediately, and the event will be reported to Novo Nordisk as below. She will be referred for continued primary care and OBGYN care.

Subjects will be carefully instructed regarding reconstitution, safe injection technique, and appropriate storage of the study drug and disposal of sharps. A study investigator will be on call 24/7 for any questions or concerns.

Persistent elevations in blood sugar after discontinuing growth hormone are not expected. However, if any subject is discontinued for fasting glucose ≥ 126 mg/dL, confirmed on repeat draw (see below), we will arrange for a repeat fasting glucose approximately 2-4 weeks after stopping growth hormone. We will arrange this to be performed either at MGH through the study or locally with the patient's primary care doctor. If this is still elevated, the patient will be referred to his/her primary care doctor for continued follow-up and, if desired, we will also arrange for follow-up with endocrinology at MGH.

Individual and Study Stopping Rules

Individuals will be discontinued from the study if

- s/he undergoes 2 dose reductions and continues to have IGF-1 SDS >2

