- s/he has fasting glucose ≥ 126 mg/dL confirmed on a repeat draw
- s/he reports significant adverse effects including significant arthralgia, myalgia, or edema

The study will be stopped if

- More than 2 individuals in the GH group have persistent fasting glucose ≥ 126 mg/dL

The study will be halted and the dosing algorithm reconsidered (and lowered) if

- More than 2 individuals in the GH group have IGF-1 SDS >2 after 2 dose reductions

Alternative Treatments

There are no FDA-approved highly effective treatments for NAFLD in young adults, and research into novel treatments is urgently needed. Vitamin E, ursodiol, and metformin are sometimes used for NAFLD, and vitamin E has been demonstrated to improve liver histology in individuals with NASH. Subjects who wish to participate and have been receiving Vitamin E or ursodiol at a stable dose for ≥ 6 months will be eligible for the study with continued use of these medications (under the ongoing care of their hepatologist) during the study. Metformin use is not allowed as it will confound assessment of glucose homeostasis. We will not ask any subject to discontinue any medication in order to participate in the study.

As we are not performing liver biopsy during the current study, the study procedures will not result in new diagnosis of NASH (which requires histology). However, subjects without known NAFLD who demonstrate $\geq 5\%$ liver fat on MRS and who have elevated ALT or AST are likely to have NASH, and, if not already under the care of a hepatologist, these subjects will be offered a clinical referral to pediatric hepatology. Subjects who are found to have labs suggesting significant liver disease (AST or ALT > 2.5x upper limit of normal (ULN) or total bilirubin > ULN) will be encouraged to seek clinical care from a hepatologist and will not be eligible for the study. AST and ALT will be carefully monitored (0, 6, 12, 18, and 24 weeks).

VIII. Potential Benefits

Participants will receive information about their nutritional and metabolic health. In addition, subjects randomized to Norditropin may experience benefits from this treatment including decrease in fat mass and possibly decreases in liver fat and systemic inflammation. All subjects will receive lifestyle counseling and information about healthy nutrition and physical activity. Further, the information obtained from this study will inform the potential use of rhGH and possibly other strategies to treat NAFLD in adolescents.

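### The stopping rules remove subjects from the study, while the follow-up rule keeps everyone who stops treatment; applied as written, the stopping rules lose primary outcomes, mainly on Norditropin

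*Combined protocol and SAP*

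**What the plan says.** **Follow-up after stopping treatment.** Section V, Study Procedures: "Subjects who discontinue treatment for any reason will be asked to continue to return for study visits per their original randomization assignment". No exception is given.

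**Individual stopping rules.** Three places use a different object:
- Section V, footnote to the Norditropin dosing table: subjects whose IGF-1 SDS stays above 2 "after 2 dose reductions will be discontinued from the study".
- Section VI, Study Drug: a subject with fasting glucose of 126 mg/dL or more has it rechecked and, "if hyperglycemia is confirmed, will be discontinued from the study".
- Section VIII, Individual and Study Stopping Rules: "Individuals will be discontinued from the study if", followed by the IGF-1 rule, the glucose rule and a third, "s/he reports significant adverse effects including significant arthralgia, myalgia, or edema".

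**Study-level rules.** The same part of Section VIII stops the study if "More than 2 individuals in the GH group have persistent fasting glucose" at or above 126 mg/dL. It halts the study, to lower the dosing algorithm, if "More than 2 individuals in the GH group have IGF-1 SDS" above 2 after two reductions.

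**Measurement and analysis.** Section V schedules liver MRS at screening and at week 24 only. Section VII makes the 24-week change in liver fat the primary endpoint and compares it by a two-sample t-test, described as intention-to-treat on the data available. Multiple imputation is a secondary option, to be considered if needed.

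**The concern.** The two instructions conflict, and site staff must choose between them each time a rule is met. If the stopping rule wins, the subject has no second MRS and no change score, and so cannot enter the primary test. The analysis labelled intention-to-treat would then be an available-case analysis, with subjects missing because of events after randomisation and mostly in one arm.

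Aim 2a is affected too. Its 24-week 2-hour glucose, HOMA-IR and Matsuda results would lack the same subjects, including any removed for high glucose. Subjects who stop drug for other reasons would still be asked back, so follow-up would depend on why treatment ended. The trial is unblinded, which is a further reason not to leave the choice to judgement.

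**Working it through.** **1. The plan's own figure.** Inputs from Section VII: 24 randomised 1:1, 19 evaluable after up to 20% discontinuation, SD 3.1, difference 4.2 points, two-sided alpha 0.05. I take 3.1 as the SD of the change.
- Standard error for 10 v 9: 3.1 × √(1/10 + 1/9) = 1.42.
- Noncentral t power: 79.4%. The stated 80% is reproduced.

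**2. Which instruction governs?** The text points both ways.
- Towards stopping drug only: the Growth Hormone text in Section VIII advises subjects with concerning side effects to come off the medication. It also times the repeat glucose from when growth hormone is stopped.
- Towards leaving the study: the wording of all three rules; Section VII, which goes from discontinuation directly to a smaller evaluable number; and the option of having that repeat glucose done by a local doctor, with no mention of continued visits or the week-24 scan.

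Nothing settles it.

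**3. Timing under the literal reading.**
- Glucose: the first check is at week 2 and a repeat draw must follow, so removal could come up to 24 − 2 = 22 weeks before the scan.
- IGF-1: reductions at weeks 2 and 4 and still above 2 at week 6, so 24 − 6 = 18 weeks before it.

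**4. Which arm.** The IGF-1 rule applies only to Norditropin. The named adverse effects are among those listed for rhGH. For glucose, Section VIII says "Fasting blood sugar will be checked at 2, 4, 6, and 12 weeks" and the Section V visit schedule adds week 18. That is four or five checks on Norditropin between baseline and week 24, against one (week 12) in controls.

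**5. How many.** The documents give no rate. The pilot had no dose reductions and no significant arthralgia, myalgia or edema (Section VI). Two 20% cuts from the starting dose give 0.5 × 0.8 × 0.8 = 0.32 mg, if there was no earlier increase. The pilot rose to 0.8 mg and reached a mean IGF-1 SDS of 0. The IGF-1 rule therefore looks hard to meet.

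**6. Precision is not the problem.** If k treated subjects are lost and all 12 controls are scanned, power for 4.2 points is 87.2% (k = 1), 85.3% (k = 2) or 80.1% (k = 4). These figures apply to the subjects who stay.

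**7. What shift would need.** Leaving out k of 12 moves the treated mean by (k/12) × g, where g is the difference in mean change between stayers and removed subjects. As a yardstick of my choosing, take 0.42 points, 10% of 4.2 and about 0.3 of the standard error in step 1. The required gap is 0.42 × 12/k:

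| k (illustration only) | gap needed, points |
|---|---|
| 1 | 5.0 |
| 2 | 2.5 |
| 4 | 1.3 |

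The documents give no liver-fat change for such subjects, so g cannot be estimated.

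**8. Cost of keeping everyone.** With 12 v 12 and an undiluted 4.2 points, power is 88.7%. If k treated subjects keep no benefit, the effect is 4.2 × (12 − k)/12.
- k = 1: 3.85 points. Power is 82.8% by formula, or 80.8% by simulation (400,000 trials) that includes the extra spread in the treated arm.
- k = 2: 3.5 points. Power is 75.3% by formula, or 70.8% by simulation.

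**The case against.** The best reply is that Section V already answers the question. Its sentence is the only one that says what happens at later visits once treatment ends, it covers every reason, and no stopping rule cancels the week-24 visit. With the drug-stop wording in Section VIII, a sensible coordinator could conclude that only the injections end. That reading is plausible, and under it nothing is lost. It is not written down, however, and three places say otherwise. The plan is also open about analysing the data available and budgets for 20% loss. That answers the loss of precision but not selective loss.

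A reader might go further than the documents allow in three ways.
- **That the result will be biased towards Norditropin.** Losing subjects who tolerate drug poorly could favour it; losing those with persistently high IGF-1 could work against it. Neither direction is established.
- **That the study-level rules cap removals at two per rule, so four of 12.** They do not. Persistent glucose is undefined and may not mean the same as confirmed on a repeat draw; Section VIII also speaks of elevations that persist after growth hormone is stopped. The IGF-1 trigger pauses the study for a lower algorithm, so removals could follow a restart. The third subject who trips a rule is removed as well. Adverse-effect stops have no cap.
- **That the power statement is wrong.** It reproduces.

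**Conclusion.** The conflict is real and touches the primary endpoint, but only if the stopping rules are applied as worded. In that case the subjects lost would be mainly on Norditropin and lost for reasons tied to exposure or tolerability. The number is probably small, with no firm upper limit in the plan. No size or direction of bias is shown. The gaps in the working say only how different removed subjects would have to be, and k = 1, 2 and 4 are illustrations. The power figures rest on 3.1 being the SD of the change, and the dilution figures also on stopped subjects keeping no benefit. This is a cheap improvement to the wording and does not show that the design fails.

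**What to change.** In the dosing-table footnote (Section V), the Study Drug text (Section VI) and the individual stopping rules (Section VIII), change removal from the study to removal from study drug for the IGF-1, glucose and adverse-effect rules. State there that the Section V follow-up sentence applies. Seek the 24-week MRS/MRI and bloods, where safe, from all randomised subjects, and analyse them in the assigned arm.

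Record drug status at week 24, because an off-drug sample does not show on-drug glucose for Aim 2a. A control subject with confirmed high glucose has no drug to stop and should be referred for care and kept in follow-up.

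Keep every individual safety criterion, both study-level rules, and the general authority in Section XI to withdraw a subject at excessive risk. Handle pregnancy separately: Section VIII stops drug and Section XI ends participation, so it needs its own clarification.

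The cost is protocol wording, a few off-drug visits that Section V already intends, and a possibly diluted effect (power about 81–83% with one treated subject keeping no benefit, 71–75% with two). The diluted effect is the one an intention-to-treat comparison estimates. The higher power from leaving stopped subjects out (85% for 10 v 12) applies to stayers only.

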Patients will arrive after an 8-hour fast. For females, urine pregnancy test will be performed prior to the start of any procedures. When possible, women with regular menses will be studied within 10 days of the onset of the menstrual cycle.

1. Within one week prior to the baseline visit, subjects will come in the fasting state for a clonidine/arginine stimulation test to assess GH secretion (see methods).
2. Interval history and physical exam
3. Indirect calorimetry in the fasting state for the first 10 randomized subjects only
4. Fasting blood sample for glucose, insulin, IGF-1, AST, ALT, GGT, lipid panel, CRP, adiponectin, CK18
5. Standard 75g oral glucose tolerance test
6. DXA for quantification of total and regional fat and lean mass, VAT and SAT
7. Anthropometrics including height, weight, waist and hip circumferences, neck, mid-arm, and mid-thigh circumferences
8. Analysis of 24-hour food recall for macro- and micronutrient composition
9. Assessment of physical activity and lifestyle habits (including alcohol consumption) using questions from the 2013 Standard High School Youth Risk Behavior Survey (YRBS)
10. Instruction on reconstituting and administering Norditropin for subjects randomized to rhGH, with first injection prior to discharge

Safety Visits (2, 4, 6, and 18 weeks, Norditropin subjects only): **(1)** Interval H&P and safety assessment; **(2)** IGF-1, fasting glucose **(3)** Collection of used study drug and dispensation of new supply.

12 Week Visit: **(1)** Interval H&P and safety assessment; **(2)** IGF-1, fasting glucose **(3)** Collection of used study drug and dispensation of new supply for Norditropin subjects; **(4)** AST and ALT.

24 Week Visit: Subjects receiving treatment will be instructed to take their final Norditropin injection the night before the visit. Girls with regular menses will be studied within 10 days of the onset of the menstrual cycle. This visit will be identical to baseline with the addition of ¹H-MRS/MRI in the fasting state prior to OGTT. (clonidine/arginine stimulation test will *not* be repeated.) Indirect calorimetry will be performed only for the first 10 randomized subjects.

VI. Methods

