Analysis will be intention-to-treat, using all available data from all subjects. Wilk-Shapiro test will be used to assess for normality of distribution of all variables, and variables that are not normally distributed will be appropriately transformed. Baseline variables will be compared between treatment groups, and any baseline variable that is statistically different between treatment groups will be adjusted for in subsequent analysis. Changes in variables measured only at baseline and 6 months, including the primary endpoint of liver fat, will be initially assessed using a two-sample t-test comparing mean changes between treatment groups. A critical alpha level of 0.05 will be used as the threshold for significance, and all statistical tests will be two-tailed. Subsequently, adjusted analyses will be performed including as covariates any baseline characteristics that differ between treatment groups and any differential changes in nutritional intake or physical activity between treatment groups over the study duration. For variables measured at ≥ 3 timepoints throughout the study (e.g., IGF-1, AST and ALT), we will analyze the longitudinal data using general linear mixed effects modeling, testing for time x treatment group interaction. The primary analysis will be an intention to treat analysis using all available data. We will consider secondary multiple imputation based analyses if necessary.

A supplementary analysis will be performed assessing stimulated growth hormone levels in response to Arginine testing. Using peak GH as the independent variable, we will assess the hypothesis that peak GH will be negatively associated with liver fat quantity.

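### Randomisation appears to precede the baseline visit of an open-label trial, so baseline-visit measures, chiefly self-reported diet and activity, may be taken with the arm known

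*Combined protocol and SAP*

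**What the plan says.** Section V, under Randomization and Study Drug, has this sentence: "After the screening visit, eligible patients who wish to participate will be randomized in a 1:1 ratio to Norditropin vs. no treatment". That paragraph also says: "The study will not be blinded and placebo will not be used". It stands between the description of screening and that of the baseline visit.

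The baseline-visit list in Section V treats subjects as already assigned:

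- Item 3: "Indirect calorimetry in the fasting state for the first 10 randomized subjects only".
- Item 10, the last item: "Instruction on reconstituting and administering Norditropin for subjects randomized to rhGH, with first injection prior to discharge".

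Before randomisation, screening provides the abdominal MRS/MRI and "blood sampling for IGF-1, CBC, HbA1c, fasting glucose, AST, ALT, total bilirubin, Hepatitis B sAg, Hepatitis C antibody". Of the scan the protocol says: "This scan will also be used to assess VAT and SAT for those eligible subjects participating in the baseline visit".

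The blood list at the baseline visit is "Fasting blood sample for glucose, insulin, IGF-1, AST, ALT, GGT, lipid panel, CRP, adiponectin, CK18". That visit also includes the OGTT, DXA, anthropometrics, 24-hour food recall and a questionnaire on activity and lifestyle. The stimulation test falls in the week before it.

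Section VII compares mean changes by t-test. It then plans adjusted analyses whose covariates are the baseline characteristics that differ between arms and "any differential changes in nutritional intake or physical activity between treatment groups over the study duration".

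**The concern.** A baseline value should not be able to depend on the assignment. If subjects know their arm when they recall their food intake or answer activity questions, they may report differently, or may already behave differently. The baseline is one half of a change score, so a shift in one arm's baseline passes directly into the difference in change between arms.

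Two uses in Section VII carry this beyond the secondary endpoints. Differential change in diet and activity is a covariate in the adjusted analyses, which include the analysis of liver fat. A baseline variable that differs significantly between arms also triggers adjustment, and that rule presumes that the values were obtained before assignment.

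Separately, a subject who leaves between randomisation and the baseline visit counts as randomised, and so belongs to the intention-to-treat population, but contributes no baseline-visit data.

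**Working it through.** **1. Order of events.** The randomisation paragraph sets only a lower limit, after screening. Item 3 of the baseline visit selects subjects by order of randomisation, and it comes ahead of the blood draw, OGTT, DXA, anthropometrics, food recall and questionnaire. It cannot be applied as written unless that order is known. Nowhere is it said that the arm is withheld until the baseline measurements are done. The visit schema is not shown in the copy reviewed, so the order is an inference, though the natural one.

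**2. What is exposed.**

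| Measure | Listed pre-treatment source | Can be taken with arm known? |
|---|---|---|
| Liver fat (primary), MRI VAT and SAT | Screening scan | No |
| HbA1c | Screening only | No |
| IGF-1, fasting glucose, AST, ALT | Screening and baseline visit | Screening value no; baseline-visit value yes |
| Insulin, 2-hour glucose, GGT, lipids, CRP, adiponectin, CK18, DXA, calorimetry | Baseline visit | Yes, but hard to influence |
| Anthropometrics | Baseline visit | Yes, some scope for influence |
| Food recall, activity and alcohol answers | Baseline visit | Yes, most open to influence |

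For the four bloods measured twice, the plan does not say which value is the baseline.

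**3. The plan's own power figure.** Inputs from Section VII: SD 3.1, difference 4.2 percentage points, two-sided alpha 0.05, 24 subjects with up to 20% loss (24 × 0.8 = 19.2, so 19 evaluable). Take the split as 9 v 10.

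- Noncentrality = 4.2 / (3.1 × √(1/9 + 1/10)) = 4.2 / (3.1 × 0.4595) = 2.95.
- With 17 degrees of freedom the critical t is 2.110, and power is 79.4%. The stated 80% is reproduced.

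Moving randomisation changes none of these inputs.

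**4. Illustration of a shifted baseline.** Suppose there is no true effect, and knowledge of the arm shifts baseline in one arm relative to the other by δ, in SDs of the change score, with no matching shift at week 24. The two-sample t-test on change then has noncentrality δ / 0.4595.

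| Assumed δ | Noncentrality | Rejection rate (nominal 5%) |
|---|---|---|
| 0.25 | 0.54 | 8.1% |
| 0.50 | 1.09 | 17.7% |

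The documents give neither a value of δ nor the interval between randomisation and the baseline visit. A shift that persisted unchanged to week 24 would cancel in the change score.

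**5. Room to move allocation.** Item 10 is the only arm-specific step of the visit, and it is the last. Item 3 depends on order of randomisation but not on the arm.

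**The case against.** The strongest reply is that little of importance is exposed. The primary endpoint, MRI VAT and five blood secondaries (IGF-1, HbA1c, fasting glucose, AST, ALT) have values from before randomisation. Laboratory assays and DXA are not open to reporting bias; they would need a real physiological change within an interval that is not stated. The diet and activity covariates enter only the later adjusted analyses, not the initial t-test. The trial is a 24-subject pilot. All of this stands and limits the point. A reader might infer that every baseline except the scan is compromised; the screening bloods show otherwise.

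The order itself can be questioned. Randomisation on arrival at the baseline visit would also fit the text, and would leave no gap for withdrawal or for a change in behaviour. Even then the recall and questionnaire would be completed with the arm known, unless it were withheld, and the protocol does not say that it is.

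A reader might also infer that early randomisation costs power on the primary endpoint through departures of subjects assigned to no treatment, and that later randomisation would restore it. The arithmetic is easy: 10 v 9 gives 79.4% and 10 v 7 gives 72.9%. The inference does not follow. Someone who leaves on learning the arm at the end of the baseline visit has no 24-week scan either, and drops out of the t-test on change just the same. The two extra losses are moreover an assumption added to a 20% allowance that the plan already makes. The lower power figure is therefore no part of this point.

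**Conclusion.** The concern holds in limited form. As written, and on the natural reading, assignment precedes the baseline-visit measurements of an unblinded trial, and nothing keeps the arm from subjects or staff until those measurements are complete. The realistic exposure is self-reported diet and activity, perhaps anthropometrics. It reaches liver fat only through the adjusted analyses; the initial comparison of liver fat is not touched.

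The size cannot be determined from the documents. The 8% and 18% rejection rates are illustrations that rest on assumed differential shifts of 0.25 and 0.5 SD of the change score, 9 v 10 evaluable, and no matching shift at week 24. They are not estimates of the bias to be expected, least of all for assays and DXA. The sample size and stated power are unaffected.

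The change is worth making because it closes an avoidable weakness at almost no cost.

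**What to change.** In Section V, state that randomisation takes place at the baseline visit after items 1 to 9 are complete and immediately before item 10. Reword the calorimetry rule, at baseline and at week 24, so that it applies to the first 10 subjects attending the baseline visit. State which value serves as baseline for IGF-1, fasting glucose, AST and ALT; after this change both candidates precede assignment.

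The change adds no visit or test and leaves the sample size as it is. Its cost is that study drug must be ready before the arm is known.

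It prevents baselines taken with the arm known, and it means that subjects who leave before or during the baseline measurements are not counted as randomised. It does not prevent withdrawal once the arm is learned, and it does not blind follow-up.
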